7.5.5.1. Mayo Risk Score

Mayo Risk Score (MRS) ([Dickson 1989](#)) is calculated and reported within the EDC system based on data entered into the eCRF. Calculation of MRS includes Investigator assessment of peripheral edema and the use of diuretic therapy, which will be assessed during adverse event and concomitant medicine review at the scheduled visits and entered into the eCRF, as well as total bilirubin, albumin, and prothrombin time results obtained from the central laboratory data.

7.6. Dose Adjustment, Interruption, and Withdrawal from Investigational Product or Study

Investigational product may be temporarily decreased (eg, from 10 mg twice weekly to 5 mg twice weekly, or from 5 mg twice weekly to 5 mg once weekly) or temporarily or permanently stopped based on tolerability concerns. Investigational product may be resumed at the maintenance dose upon resolution of gastroenteritis or worsening renal function or dehydration if there is no evidence of liver injury. For rechallenge following all other dose interruptions (see Table 7), investigational product should be initiated at a lower dose and subjects monitored more frequently with up-titration considered based on tolerability.

Adjustments, interruptions, discontinuation, and any rechallenge of investigational product should be implemented per the criteria outlined in Table 7. Subjects that discontinue investigational product are expected to continue in the study (and follow the regular visit schedule) until the end of the study, and the study will terminate at the time when the needed number of adjudicated events has accrued. If a subject reaches an outcome event, he or she should continue the regular visit schedule and continue taking investigational product as long as the subject has not met any of the criteria for mandatory interruption of investigational product outlined in Table 7, and the Investigator assesses it as safe. In general, subjects should be strongly encouraged to both stay on investigational product and remain in the study until study termination.

Table 7: Criteria for Dose Adjustment, Interruption, Discontinuation and Rechallenge

DOSE ADJUSTMENT		
Criteria	Action Taken with IP	Adjustment
Progress to cirrhosis and have CP A cirrhosis (CP score <7)	Adjust to a maximum daily dose of 10 mg (or equivalent placebo) in a blinded fashion	Not applicable. Remain at maximum daily dose of 10 mg (or equivalent placebo) for remainder of study.
Progress to CP B or C cirrhosis (CP score ≥7)	Adjust IP dose to 5 mg once weekly, then titrate to a maximum 10 mg twice weekly (at least 3 days apart).	After a minimum of 3 months, if at a lower dose, subjects may titrate to a maximum IP dose of 10 mg twice weekly per Investigator discretion.
New onset Severe Pruritus	Drug holiday or less frequent dosing	Return to original dose regimen if tolerated
DOSE INTERRUPTION		
Criteria	Action Taken with IP^a	Rechallenge^b
If liver biochemistries indicative of suspected hepatic injury are identified as exceeding upper threshold criteria and require immediate interruption (see Part A of Table 4) ^c	Interrupt immediately upon initial observation	Patient may be rechallenged after a minimum of 30 days if fully resolved OR stable and approved by the Medical Monitor and Investigator.
Other liver biochemistries indicative of suspected hepatic injury are outside upper threshold criteria upon repeat testing as defined in Part A of Table 4 ^d	Interrupt after confirmation by repeat testing	

Liver biochemistries indicative of potential hepatic decompensation in the absence of symptoms (see Part B of Table 4) ^e	Closely monitor until normalization or stabilization. If values continue to increase relative to the baseline value, interrupt	
Clinical events indicative of hepatic decompensation (see Part B of Table 5)	Closely monitor until normalization	The subject may be rechallenged after a minimum of 30 days if fully resolved OR stable and approved by the Medical Monitor and Investigator. IP should be re-initiated at a lower dose (or lower dose frequency) and titrated per Investigator discretion.
Gastroenteritis (established severe abdominal pain, vomiting, diarrhea for more than 4 days)	Interrupt	If no evidence of liver injury is detected, IP may be restarted at the same dose after resolution of intercurrent illness.
Evidence of worsening of renal function or dehydration	Interrupt	
Pregnancy	Interrupt	Patient should continue with the study visit schedule. The subject may re-start IP when she is no longer pregnant or breastfeeding (if applicable) at the discretion of the Investigator and after discussion with the Medical Monitor
DOSE DISCONTINUATION		
Criteria	Action Taken with IP	Rechallenge
If INR increases ≥ 2.0 in absence of clinical symptoms criteria (unless due to vitamin K deficiency)	Discontinue / No Rechallenge	Discontinue IP permanently and continue to return for scheduled study visits for safety follow up.
If total bilirubin, thresholds (Part B of Table 4) are observed in the presence of clinical symptoms of cholestatic hepatitis or hepatic encephalopathy ^f		Monitor closely for clinical outcomes per protocol.
Multi-Organ failure requiring hospitalization		Continue to return for scheduled study visits for safety follow up. Monitor closely for clinical outcomes according to protocol assessments.
Liver transplantation		

Fully resolved = Return to baseline levels or return to within normal limits (WNL). IP = investigational product

^a If subject is unable to be evaluated promptly, study drug must be immediately interrupted.

^b Requires complete documentation of complete resolution or normal/baseline results based on laboratory parameters and symptoms.

^c Total bilirubin baseline \leq ULN and Postbaseline $\geq 3x$ baseline, Baseline $>$ ULN and Postbaseline $\geq 2x$ Baseline, ALT or AST $> 3x$ baseline (and $>$ ULN)

^d ALT or AST $\geq 2x$ baseline, albumin < 3.2 g/L or electrolytes (sodium < 130 mEq/L).

^e Conjugated bilirubin > 0.5 mg/dL increase from baseline; Total bilirubin Baseline \leq ULN and 1.5 mg/dL increase from baseline OR Baseline $>$ ULN and 1.0 mg/dL increase from baseline; INR > 0.3 increase from baseline

^f If INR increases ≥ 2.0 in the absence of clinical symptoms or if conjugated bilirubin or total bilirubin, thresholds OR an INR increase from baseline of ≥ 1.5 are observed in the presence of clinical symptoms of cholestatic hepatitis or hepatic encephalopathy.

^g Multi organ failure including hepatorenal syndrome Type 1 or Type 2 and acute kidney injury, hepatopulmonary syndrome, or portopulmonary syndrome.

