7.5. Monitoring and Management of Potential Hepatic Injury and/or Disease Progression

Given the chronic nature of PBC, it is important to monitor for potential hepatic injury, disease progression and/or hepatic decompensation. Child-Pugh and MELD scores will be reviewed at each visit where labs are drawn ([Table 1](#)). Child Pugh Scores should only be applied in patients who have evidence of cirrhosis at screening or demonstrate evidence of cirrhosis at screening or progression to cirrhosis during the study based on criteria presented in [Section 7.5.4](#). In addition, adverse events, signs and symptoms of potential hepatic injury or decompensation, and laboratory values will also be reviewed at regular intervals as described in [Section 7.1.2](#). Based on the assessments of signs and symptoms of hepatic injury and liver biochemistry, the investigational product may be interrupted or discontinued per criteria discussed in [Section 7.5.2](#) and [Section 7.5.3](#), and close monitoring procedures will be implemented ([Section 7.7](#)).

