Baseline $>$ ULN and 1.0 mg/dL increase from baseline		
INR^b	Closely monitor until normalization or stabilization.	The subject may be rechallenged after a minimum of 30 days if fully resolved OR stable and approved by the Medical Monitor and Investigator.
$>$ 0.3unit increase from baseline	If values continue to increase relative to the baseline value, interrupt IP.	If laboratory values do not normalize, IP should not be restarted.
\geq 2.0 unless due to vitamin K deficiency	Discontinue IP permanently	Continue to return for scheduled study visits for safety follow up. Monitor closely for clinical outcomes per protocol.
C. Laboratory Criteria for Monitoring Potential Hepatic Decompensation in the Presence of Clinical Symptoms		
Total bilirubin thresholds defined in Part B OR an INR increase from baseline of \geq 1.5 are observed in the presence of clinical symptoms of cholestatic hepatitis or hepatic encephalopathy ^c	Discontinue IP permanently	Continue to return for scheduled study visits for safety follow up. Monitor closely for clinical outcomes per protocol.

IP = investigational product

^a Sodium will be measured as an assessment of liver failure (hyponatremia).

^b Does not apply in subjects on anti-coagulants.

^c Symptoms of cholestatic hepatitis includes dark urine and jaundice. Symptoms of hepatic encephalopathy may include lack of awareness, shortened attention span, lethargy, gross disorientation, or coma (unresponsive to verbal or noxious stimuli)

It should be noted that it is difficult to recognize every potential marker of hepatic or renal deterioration. There is no substitute for good medical judgment. Investigators will be reminded to be cautious and mindful in their evaluation of subjects' symptoms, signs, and laboratory results. However, for example, a single abnormal laboratory analyte result may be artefactual; accordingly, Investigators will be allowed to implement an alternate follow-up procedure if

considered appropriate based on their medical judgement but only after documented agreement with the Sponsor's Medical Monitor.

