
 • Liver failure defined as worsening synthetic function that is persistently worse relative to baseline and/or progressive over time (see Table 4, Part B)^a • Variceal bleeding or recurrent variceal bleeding^b documented by endoscopy or accompanied by anemia or melena with a hemoglobin drop of ≥ 2 g/dL • Ascites^c including: 
 ○ Worsening – requires increase in drug therapy or surgical intervention (paracentesis or shunt procedure) ○ Refractory ascites – unresponsive to medication; patient not candidate for transjugular intrahepatic portosystemic shunt (TIPS) or shunt; requires large volume paracentesis ○ Hyponatremia (≤ 125 mEq/L) secondary to ascites • Spontaneous Bacterial Peritonitis • Hepatic Encephalopathy, Grade ≥ 2 • Any liver-related event requiring hospitalization and treatment (except multi-organ failure) • Hepatorenal syndrome Type 1 or Type 2 and acute kidney injury, hepatopulmonary syndrome, or portopulmonary syndrome 	
Closely monitor until normalization or stabilization.
 
The patient may be rechallenged after a minimum of 30 days if fully resolved OR stable and approved by the Medical Monitor and Investigator
 
IP should be re-initiated at a lower dose (or lower dose frequency) and titrated per Investigator discretion.

^a Patients experiencing INR ≥ 2.0 unless due to vitamin K deficiency should be discontinued from IP permanently without rechallenge and should to return for scheduled study visits for safety follow up.

^b Endoscopic confirmation of gastric or duodenal varices without evidence of bleeding should be closely monitored; investigational product may be interrupted at Investigator discretion.

^c New onset ascites requiring treatment should be closely monitored; investigational product may be interrupted at Investigator discretion.

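### Table 7 does not reproduce the hepatic stopping criteria it draws from Tables 4 and 5: the INR stop, albumin and conjugated bilirubin all differ

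*Protocol*

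**What the plan says.** Two sets of criteria are made operative. Section 7.5 says "the investigational product may be interrupted or discontinued per criteria discussed in" Sections 7.5.2 and 7.5.3, that is, Tables 4 and 5. Section 7.6 says "Adjustments, interruptions, discontinuation, and any rechallenge of investigational product should be implemented per the criteria outlined in Table 7". No sentence says which prevails.

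**INR, permanent stop**
- Table 4 Part B (Section 7.5.2): an INR of 2.0 or more, "unless due to vitamin K deficiency". Footnote b, attached to the INR heading, adds "Does not apply in subjects on anti-coagulants".
- Table 5 footnote a (Section 7.5.3): subjects with an INR of 2.0 or more "unless due to vitamin K deficiency should be discontinued from IP permanently without rechallenge". It has no anticoagulant exemption.
- Table 7 discontinuation row (Section 7.6): "If INR increases" 2.0 or more "in absence of clinical symptoms criteria (unless due to vitamin K deficiency"). It has no anticoagulant exemption.
- Table 7 footnote f: the same verb and the same 2.0, with neither exception.

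**Albumin.** Table 7 footnote d lists albumin below 3.2 g/L. It annotates the repeat-test interruption row, which takes its criteria from Table 4 Part A.

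**Conjugated bilirubin.** The Table 7 interruption row for "Liver biochemistries indicative of potential hepatic decompensation in the absence of symptoms (see Part B of Table 4") carries footnote e, which adds a conjugated bilirubin rise above 0.5 mg/dL. Footnote f carries conjugated bilirubin into the permanent stop for symptomatic subjects.

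**The concern.** These thresholds decide when drug is interrupted or stopped for good in a hepatic-safety setting. A site that follows Table 7's cross-reference to Part B of Table 4 finds a permanent stop at an INR value of 2.0. A site that reads only the Table 7 discontinuation row or footnote f cannot tell whether a value or a rise is meant.

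The missing exemption matters separately. Section 9.2 permits warfarin and asks that its dose be adjusted to hold INR in a target range. If that range reaches 2.0, a value rule without Table 4 footnote b permanently stops a subject whose anticoagulation is working as intended.

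For albumin, either an intended trigger has been disabled by a unit error or a stray criterion has been left in. For conjugated bilirubin, a symptomatic subject may be stopped permanently under footnote f but not under Table 4 Part C or under the row that footnote f annotates.

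**Working it through.** All text compared is the current Version 5 text, not the amendment history. No sample size or power figure is involved, so the check is a side-by-side reading plus one unit conversion.

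**1. INR permanent stop**

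| Statement | Form | Vitamin K exception | Anticoagulant exemption |
|---|---|---|---|
| Table 4 Part B with footnote b | value | yes | yes |
| Table 5 footnote a | value | yes | no |
| Table 7 discontinuation row | increases | yes | no |
| Table 7 footnote f | increases | no | no |
| Count | value 2 of 4 | 3 of 4 | 1 of 4 |

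No two rows match on all three features.

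A dropped *to* is the likely explanation for the verb. Where footnotes e and f clearly mean a change, they say that it is measured from baseline. The ambiguity is still real, because footnote f uses a genuine INR rise (1.5 or more from baseline) in the same sentence. The protocol gives no baseline INR, so the size of the gap rests on an assumption:
- Value reading: stop at 2.0.
- Rise reading, assumed baseline 1.0: 1.0 + 2.0 = 3.0.
- Rise reading, assumed baselines 0.9 to 1.3: 0.9 + 2.0 = 2.9 to 1.3 + 2.0 = 3.3.

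The missing exemption does not depend on this choice for Table 5 footnote a, which is plainly a value rule.

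**2. Albumin**

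Inputs: 3.2 g/L (Table 7 footnote d); reference range 33 to 49 g/L, equal to 3.3 to 4.9 g/dL (Appendix C, ages 18 to 69); 1 g/dL = 10 g/L.
- As printed: 3.2 / 10 = 0.32 g/dL, and 3.2 / 33 = 0.097, or 9.7% of the lower limit.
- If g/dL was meant: 3.2 × 10 = 32 g/L, just below the lower limit of 33 g/L.

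Table 6 gives its worst Child-Pugh albumin score below 28 g/L, which also supports g/dL as the intended unit. Table 4 Part A lists total bilirubin, ALT or AST, and sodium. It has no albumin row, and neither does the note to the Figure 2 algorithm.

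**3. Conjugated bilirubin**

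| Place | Names conjugated bilirubin |
|---|---|
| Table 4 Part B | no |
| Table 4 Part C | no |
| Table 7 symptomatic stop row | no (total bilirubin only) |
| Table 7 footnote e | yes (rise above 0.5 mg/dL) |
| Table 7 footnote f | yes (permanent stop) |

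Footnote f therefore differs both from Table 4 and from the row it annotates. Here the footnotes are the stricter version. The analyte is in the Table 12 chemistry panel, so the conflict can arise in practice.

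**The case against.** The strongest reply is that Table 7 defers to Table 4. Section 7.5.2 names Table 4 as the place for analyte thresholds, and several Table 7 rows cite Table 4 or Table 5. On that reading Table 7 sets actions, Table 4 sets thresholds, and the extra footnote items are stray annotations. The INR row also echoes the title of Table 4 Part B, where the value rule sits. Table 5 footnote a hangs on a liver-failure row that points back to Table 4 Part B, so a stable subject on warfarin is not its target.

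The practical effect is also limited. An INR rise above 0.3 already brings close monitoring, and interruption if it continues. Investigators may use an alternate follow-up with documented Medical Monitor agreement. An albumin trigger that cannot fire loses nothing relative to Table 4, and the conjugated bilirubin difference errs toward stopping drug.

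Much of this stands as mitigation. A value of 2.0 is probably what was meant, and the consequences are softened. It does not remove the defect. Section 7.6 directs sites to Table 7, and the INR discontinuation row cites no other table. The Section 7.5.2 sentence about Table 4 speaks of thresholds that trigger repeat testing and evaluation, not of which stopping rule prevails. Medical Monitor discretion does not tell a site which criterion applies.

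**Conclusion.** The concern holds and should be fixed. The INR permanent stop appears in four places with no two in full agreement, and the anticoagulant exemption appears in only one. This is an ambiguous or conflicting rule rather than a clear second threshold. The albumin criterion is wrong as printed by a factor of ten if g/dL was intended, and it has no counterpart in the table its row cites. Conjugated bilirubin is in two footnotes and in none of the three criteria they should match.

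Two assumptions are involved. That g/dL was intended is an inference, strongly supported by Appendix C and Table 6. The harm to subjects on warfarin applies only if their target INR range reaches 2.0; the protocol gives no range and no count of such subjects. Close monitoring and Medical Monitor involvement apply under every version. Power and the primary analysis are unaffected.

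**What to change.** - **INR:** reword the Table 7 row and footnote f to an INR value of 2.0 or more, excepting vitamin K deficiency and not applying to subjects on anticoagulants (Table 4 footnote b). Carry the same exemption in Table 5 footnote a.
- **Albumin:** either delete it from footnote d, or correct it to below 3.2 g/dL (32 g/L) and add it to Table 4 Part A.
- **Conjugated bilirubin:** decide whether it is a criterion, then make Table 4 Parts B and C, the Table 7 stop row, and footnotes e and f say the same.
- **Precedence:** add one sentence stating which table governs if they differ.

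The cost is a clarification letter or minor amendment, a short site notice, and a check of any laboratory alerts programmed from the Table 7 footnotes. Sample size and analysis do not change.

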- Unscheduled visits as needed in the event of signs or symptoms of suspected hepatic injury or decompensation or if laboratory alerts have been triggered

It is important that the laboratory assessments be completed as required and that the central laboratory be used for assessments whenever possible. In the event that a subject cannot return to the clinic for a scheduled or unscheduled visit, or there is an event that triggers a need for an immediate assessment, the use of a local lab is permissible at the discretion of the Investigator. In these cases, the Investigator will obtain the laboratory results and the laboratory normal ranges.

The process for assessing criteria is presented in Figure 2, and the specific threshold(s) for each laboratory analyte to trigger mandatory repeat testing and, potentially a complete subject evaluation (depending on the repeat result) are summarized in Table 4.

Figure 2: DILI Management Algorithm

IP: Investigational Product

DILI = drug-induced liver injury; IP = Investigational Product

Note: Other laboratory criteria include: ALT, AST, total bilirubin, INR, and electrolytes (sodium).

Table 4: Liver Laboratory Criteria for Monitoring of Suspected Hepatic Injury or Potential Hepatic Decompensation and Criteria for Interruption or Discontinuation of Investigational Product

A. Laboratory Criteria for Monitoring Suspected Hepatic Injury		
Laboratory Parameter	Action Taken	Rechallenging Criteria
Total Bilirubin		If a subject interrupts IP, they may be rechallenged after a minimum of 30 days if fully resolved OR stable and approved by the Medical Monitor and Investigator.
Baseline \leq ULN and \geq 3x baseline	Interrupt IP	
Baseline $>$ ULN and \geq 2x Baseline	Interrupt IP	
ALT or AST		
$>$ 3x baseline (and $>$ ULN)	Interrupt IP	
\geq 2x baseline	Repeat Test in 2 to 3 days, interrupt IP if still elevated	
Electrolytes^a		
Sodium $<$ 130 mEq/L	Repeat Test in 2 to 3 days, interrupt IP if still below threshold	
B. Laboratory Criteria for Monitoring Potential Hepatic Decompensation (Absence of Clinical Symptoms)		
Total Bilirubin	Closely monitor until normalization or stabilization.	The subject may be rechallenged after a minimum of 30 days if fully resolved OR stable and approved by the Medical Monitor and Investigator.
Baseline \leq ULN and 1.5 mg/dL increase from baseline	If values continue to increase relative to the baseline value, interrupt IP.	If laboratory values do not normalize, IP should not be restarted.

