9.2. Concomitant Medications

Concomitant medications (other than prohibited concomitant medications listed in [Section 9.2.1](#)) will be used at the discretion of the usual care provider (or Investigator if also the usual care provider). Relevant information about all concomitant medications (including prescribed, over-the-counter, or herbal preparations) taken prior to (ie, within 30 days of Screening) and during the study must be recorded in the source documents and CRF, as well as any dose or dose regimen changes that occur during the study. Concomitant medications should be stable prior to Day 0.

Drug Interactions

Subjects taking bile acid sequestrants (BAS, including cholestyramine and its derivatives, colestipol, colesevelam, or other sequestrants) or aluminum hydroxide- or smectite-containing antacids should be instructed to stagger their dosing of investigational product and UDCA, ensuring at least 4 hours between doses of the BAS and/or these antacids and the investigational

product (and UDCA; ie, BAS should be administered at minimum 4 hours before or 4 hours after investigational product administration).

OCA taken concomitantly with warfarin may result in decreased INR levels, therefore, INR should be monitored and the dosage of warfarin adjusted, as needed during treatment with OCA and after cessation of OCA, to maintain the target INR range.

The effect of OCA on drug metabolizing enzymes has been evaluated in both in vitro and clinical studies. The PK profile of caffeine, a sensitive CYP1A2 substrate probe, showed weak effect of OCA on CYP1A2. Based on these results, OCA may increase the exposure of narrow therapeutic index drugs that are substrates for CYP1A2, such as theophylline and tizanidine.

Information related to additional drug-drug interaction (DDI) studies is available in the current version of the Investigator's Brochure (IB). The aforementioned sections of the IB should be referred to during the course of the study, and are accessible to Investigators to help facilitate the assessment of potential drug-drug interactions with OCA that may be observed in study subjects.

PBC-Specific Therapy

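### Table 7 orders a permanent stop at INR ≥2.0 without the anticoagulant exemption that Table 4 gives for the same stop, and both tables are operative

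*Protocol*

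**What the plan says.** **Table 4 (Section 7.5.2), Part B.** Two INR criteria sit under one INR heading: a rise of more than 0.3 from baseline, and a value of 2.0 or more not due to vitamin K deficiency. The second requires permanent discontinuation. The heading carries footnote b: "Does not apply in subjects on anti-coagulants". The exemption therefore covers both criteria.

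**Table 7 (Section 7.6), dose discontinuation.** The INR row orders discontinuation with no rechallenge if INR increases ≥2.0 "in absence of clinical symptoms criteria (unless due to vitamin K deficiency"). Footnote f repeats the ≥2.0 trigger "in the absence of clinical symptoms or if conjugated bilirubin or total bilirubin, thresholds OR an INR increase from baseline of" ≥1.5 with symptoms. In that footnote the ≥2.0 trigger has no exception, not even for vitamin K deficiency. None of Table 7's footnotes mentions anticoagulants.

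**Which table governs.** Section 7.5 says "the investigational product may be interrupted or discontinued per criteria discussed in" Sections 7.5.2 and 7.5.3, and the title of Table 4 includes "Criteria for Interruption or Discontinuation of Investigational Product". Section 7.6 says that adjustments, interruptions, discontinuation and rechallenge "should be implemented per the criteria outlined in Table 7". No order of precedence is given.

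**Anticoagulants.** Section 9.2 provides for concomitant warfarin, with INR monitored and the dose adjusted "to maintain the target INR range".

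**The concern.** In a subject on warfarin, a raised INR is the intended effect of the co-medication and says little about hepatic synthetic function. Table 4 recognises this. So does the cirrhosis definition in Section 7.5.4.1, which sets aside INR elevation caused by antithrombotic agents. Table 7 does not, so two sites following different tables could treat identical subjects differently. One would keep randomised drug running and the other would stop it for good.

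The stop is permanent, in a trial expected to last about 10 years whose protocol strongly encourages subjects to stay on drug. What is at stake is exposure to assigned treatment, lost for a reason unrelated to the liver. Outcome data are not at stake, because subjects off drug are expected to remain in follow-up.

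The same Table 7 row has a second defect. It speaks of INR increasing by ≥2.0, whereas Table 4 and Table 5 footnote a treat 2.0 as a level. For subjects not on anticoagulants, the literal reading would delay a safety stop.

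**Working it through.** The protocol states no figure that can be reproduced here. The check is a comparison of texts, followed by simple arithmetic on where each rule acts.

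**Side by side, for an asymptomatic subject on an anticoagulant**

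| Place | Trigger | Anticoagulant exemption | Vitamin K exception | Action |
|---|---|---|---|---|
| Table 4 Part B | INR level ≥2.0 | Yes (footnote b) | Yes | None for this subject |
| Table 7 INR row | INR increases ≥2.0 | No | Yes | Permanent stop, no rechallenge |
| Table 7 footnote f, ≥2.0 part | INR increases ≥2.0 | No | No | Permanent stop |

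**Can the exemption be read into Table 7 by cross-reference?** The neighbouring laboratory rows of Table 7 cite Part A or Part B of Table 4; the INR row cites neither. Footnote f is attached to a row that cites Part B only for the total bilirubin thresholds, so footnote b does not reach its INR clause.

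**Entries not counted as contradictions.** Table 7 footnote e (INR rise >0.3) and Table 5 footnote a ("unless due to vitamin K deficiency should be discontinued from IP permanently without rechallenge") also lack the exemption. They belong to entries that refer to Table 4 Part B, so the exemption can be read in.

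**Where the rules act.** Assumptions, none of them given in the protocol: target INR 2.0–3.0; baseline INR 1.0 (range 0.9–1.2) for a subject who starts an anticoagulant during the study; baseline 2.0–3.0 for a subject already at target.

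- Table 4 Part B: no action at any INR.
- Table 7 read as a level: stop from INR 2.0, which is the lower end of the target range. All of 2.0–3.0 triggers, whatever the baseline.
- Table 7 read as an increase, threshold = baseline + 2.0:
  - new starter: 1.0 + 2.0 = 3.0 (0.9 + 2.0 = 2.9 to 1.2 + 2.0 = 3.2), at or close to the top of the target range;
  - already at target: 2.0 + 2.0 = 4.0 to 3.0 + 2.0 = 5.0, which is 1.0 to 2.0 above the top of the range, so there is no conflict while INR stays at target.

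**What still protects these subjects.** Table 4 Part C (INR increase ≥1.5 with clinical symptoms) carries no exemption. Threshold = baseline + 1.5:

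- new starter: 1.0 + 1.5 = 2.5 (2.4 to 2.7);
- already at target: 3.5 to 4.5.

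**The case against.** The best case on the other side is that Table 7 summarises Table 4. The INR row has the same 2.0 threshold, the same vitamin K exception and the same permanent stop, and its odd phrasing about absent symptoms echoes the Part B heading. A careful investigator could take Table 4 as the full rule, exemption included. Below Table 4, the protocol also allows an alternative follow-up procedure after documented agreement with the Medical Monitor. Section 8.4.1 encourages contact with the Sponsor before a subject is discontinued. The MELD >12 exclusion in Section 8.3, with MELD calculated partly from coagulation results, may keep out some subjects already at target INR. Where the tables differ, Table 7 errs towards stopping a drug for which hepatic decompensation has been reported (Section 5.7). Follow-up continues after a stop, and the ITT analysis is by randomised treatment.

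Much of this stands as a limit on size. The omission may well be a transcription gap, the number affected may be very small, and no endpoint, sample size or error rate changes. It does not remove the conflict. No text makes Table 4 prevail, and the wording in Section 7.6 is, if anything, the firmer of the two. Agreement with the Medical Monitor is case by case, and the example given is a possibly artefactual single result, whereas a therapeutic INR is persistent and expected.

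A narrower objection is that footnote f should be excused on the same ground as footnote e and Table 5 footnote a. It fails because the row carrying footnote f cites Part B for bilirubin only.

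**Conclusion.** The concern holds. For an asymptomatic subject on an anticoagulant, Table 4 exempts and Table 7 stops permanently. Both tables are operative and nothing ranks them. The wording of 2.0 as an increase in Table 7 is a separate error in a safety threshold.

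On an assumed target of 2.0–3.0, the conflict covers the whole target range if 2.0 is a level, as Table 4 and Table 5 footnote a have it. If the word increase is taken literally, it covers only new starters near INR 3.0. How many subjects this affects cannot be derived from the protocol. The consequence is loss of exposure to assigned treatment, with outcome data retained. The wording should be corrected, but the validity of the primary analysis does not turn on it.

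**What to change.** In a protocol amendment:

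1. Repeat the Table 4 footnote b exemption in the Table 7 INR discontinuation row and in the ≥2.0 part of Table 7 footnote f.
2. For consistency only, add it to the INR part of Table 7 footnote e and to Table 5 footnote a.
3. If no exemption is intended, delete Table 4 footnote b instead, so that one rule applies throughout.
4. State in Table 7 that 2.0 is an INR level.
5. Leave Table 4 Part C unchanged, so that subjects on anticoagulants who develop symptoms remain covered.

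The cost is amendment wording. No visits, tests or patients are added.
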